7.2.7 Need for Oxygen Supplement During the Trial

This endpoint will be assessed through the recordings of concomitant medication. The two medication classes V03AN and R07A will be selected.

Number of subjects requiring oxygen supplement any time during trial will be summarized by treatment and listed.

The summary will be repeated for oxygen supplement

- ongoing at baseline
- ongoing at end of trial
- ongoing at both baseline and end of trial
- started after baseline and stopped before end of trial

The listing will include further details as flow rate and regimen (dose, unit, route and frequency) as well as timing compared to baseline and end of trial (ongoing or stopped etc).

7.2.8 Overall Clinical Assessment

Overall clinical assessment consists of two endpoints as described below. Both endpoints will be summarized by treatment and visit.

- Status of aPAP (in remission, improving, stable or progressive)
- Requirement for treatment since last visit (no treatment required, treatment with inhaled molgramostim required, Whole Lung Lavage, oxygen supplementation or other treatment required)

7.3 Exploratory Endpoint

The exploratory endpoint is

- GM-CSF levels before and 2 hours after dosing

All values of GM-CSF above lower level of quantification (LLOQ) will be listed.

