The first clinical trial with molgramostim nebuliser solution has been completed (MOL-001). This was a phase I trial to investigate the effects of molgramostim nebuliser solution in healthy adult subjects. The trial was a randomised, double-blind, placebo-controlled, single ascending dose (SAD) and multiple ascending dose (MAD) trial to assess the safety, tolerability, pharmacokinetics, and pharmacodynamics in 42 adults; non-tobacco using male and non-child bearing female subjects. In the SAD part, 18 subjects were included with four subjects in each of the three SAD dose levels (150 µg, 300 µg and 600 µg) and six receiving placebo. In the MAD part, 24 subjects were included with nine subjects in each of the two MAD dose levels (300 µg or 600 µg) and six receiving placebo once daily for six days.

All 42 subjects enrolled completed the trial. GM-CSF was not measurable in serum before trial drug administration. In the SAD part, GM-CSF was absorbed into systemic circulation with time of maximum plasma concentration (t_{max}) of 2 hours after inhalation of molgramostim nebuliser solution, however, at picogram levels 50-100 times lower than has been observed after similar doses of sargramostim administered intravenously. Total systemic exposure (AUC_{last}) increased with dose ranging between 13 and 138 pg•h/mL and maximum measurable plasma concentrations (C_{max}) ranged between 9.1 and 41 pg/mL. C_{max} was similar for the 300 and 600 µg dose levels. In the MAD part, despite the short half-life of approximately 4 hours where GM-CSF levels returned to

levels below quantification limits after each dose, there was evidence of some accumulation after multiple dosing. C_{max} increased from 32 pg/mL on Day 1 to 90 pg/mL on Day 6 for the 300 µg dose level and from 96 pg/mL to 251 pg/mL from Days 1 to 6 for the 600 µg dose level. Likewise, AUC_{last} increased from 97 to 248 pg•h/mL from Days 1 to 6 for the 300 µg dose level and from 350 to 802 pg•h/mL for the 600 µg dose level. Minimum measurable plasma concentrations (C_{min}) on Day 6 were 3.6 and 5.1 pg/mL measured at 8 and 12 hours, respectively for the 300 and 600 µg dose levels.

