5.3.3. Exploratory Endpoints

- GM-CSF levels before and 2 hours after dosing

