10.8.5.1. PK assessment (Only for Italy)

The subjects enrolled in Italy will have Visits 1 - 6 scheduled for an on-treatment week during the allowed window of +/- 4 weeks. On the day of the visit, IMP dosing will be conducted at the site.

Two serum samples for analysis of GM-CSF will be collected at each of these visits. The first sample will be taken just prior to inhalation of molgramostim. The second sample will be taken 2 hours post dosing, (+/- 10 minutes). Samples will be shipped to a central laboratory for analysis. Further description of sample collection, processing, shipment and analyzing will be available in the laboratory manual. Timing of dose on the day before and on the day of sampling will be recorded in the eCRF.

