11. STATISTICS

No formal sample size calculation was done as this is an open-label extension trial. Up to 90 subjects will be included.

Data will be summarised using summary statistics. Continuous data will be presented with the number of observations, mean value, standard deviation, minimum, quartile 1, median, quartile 3 and maximum value. Categorical data will be presented as counts and percentages. The data will be presented by visit in tables and graphs. Individual subject data will be listed. Further details of all analyses will be given in the statistical analysis plan.

No “analysis sets” (intention to treat, per protocol, etc.) are defined. All subjects will be included in the analyses/data presentations (equivalent to a Full Analysis Set).

Only recorded data will be analysed/presented and any subjects who have missing data will only have observed data reported, with no imputation for missing data.

Interim cuts of data may be done on a yearly basis and as needed for regulatory purposes (e.g. 120-day safety update).

Data listings will show all recorded data.

Data from the trial is planned to be combined with relevant data from the IMPALA trial; these combined analyses will be reported separately.

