- Listing 16.2.6.8 Individual overall clinical assessments (all subjects)
- Listing 16.2.6.9 Individual GM-CSF measurements above lower level of quantification (all subjects)
- Listing 16.2.7.1 Adverse events (all subjects)
- Listing 16.2.7.2 Serious adverse events (all subjects)

Listing 16.2.7.3 Adverse drug reactions (all subjects)

Listing 16.2.7.4 Adverse events leading to treatment discontinuation (all subjects)

Listing 16.2.8.1 Individual haematology (all subjects)

Listing 16.2.8.2 Individual clinical chemistry (all subjects)

Listing 16.2.9.1 Individual vital signs (all subjects)

Listing 16.2.9.2 Individual electrocardiogram (all subjects)

Listing 16.2.10.1 Individual CT scans (all subjects)

13 List of Tables

Section 14.1

Table 14.1.1 Subject disposition (full analysis set)

Table 14.1.2 Number of subjects by visit (full analysis set)

Table 14.1.3 Baseline demographics (full analysis set)

Table 14.1.4 Medical history (full analysis set)

Table 14.1.5 Summary of exposure (months) (safety analysis set)

Table 14.1.6 Summary of cumulative exposure (safety analysis set)

Table 14.1.7 Summary of relative exposure (safety analysis set)

Table 14.1.8 Summary of last visit attended (full analysis set)

Table 14.1.9 Concomitant medication (safety analysis set)

Table 14.1.10. Summary of missed key secondary endpoints assessments due to COVID-19 pandemic (safety analysis set)

Table 14.1.11 Summary of alternative endpoint ascertainment due to COVID-19 pandemic (safety analysis set)

Section 14.2

(14.2.1: Blood gas analysis endpoints)

Table 14.2.1.1 Summary of (A-a)DO₂ (mmHg) (full analysis set)

Table 14.2.1.2 Summary of change from baseline in (A-a)DO₂ (mmHg) (full analysis set)

(14.2.2: 6 minutes walking test endpoints)

Table 14.2.2.1 Summary of 6 minutes walking distance (m) (full analysis set)

Table 14.2.2.2 Summary of change from baseline in 6 minutes walking distance (m) (full analysis set)

Table 14.2.2.3 Summary of pre-walk dyspnoea score (Borg CR10) (full analysis set)

Table 14.2.2.4 Summary of change from baseline in 6 minutes walking distance (m) (full analysis set)

Table 14.2.2.5 Summary of post-walk dyspnoea score (Borg CR10) (full analysis set)

Table 14.2.2.6 Summary of change from baseline in dyspnoea score (Borg CR10) (full analysis set)

Table 14.2.2.7 Summary of SpO₂ at start of walk (%) (full analysis set)

Table 14.2.2.8 Summary of change from baseline in SpO₂ at start of walk (%) (full analysis set)

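### GM-CSF results at or below the LLOQ appear in no planned output, contrary to protocol section 11 and undeclared in the SAP (minor)

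*SAP*

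**What the plan says.** - **Endpoint.** Protocol 5.3.3 defines it as "GM-CSF levels before and 2 hours after dosing". Protocol 4.2 gives the purpose: to characterise possible systemic adverse effects in a subset, the Italian subjects.
- **Sampling.** Protocol 10.8.5.1: "The subjects enrolled in Italy will have Visits 1 - 6 scheduled for an on-treatment week", and "Two serum samples for analysis of GM-CSF will be collected at each of these visits".
- **Planned output.** SAP 7.3: "All values of GM-CSF above lower level of quantification (LLOQ) will be listed". The SAP's list of listings (section 12) repeats the restriction in the title of Listing 16.2.6.9: "Individual GM-CSF measurements above lower level of quantification (all subjects"). The SAP's lists of tables and figures contain no GM-CSF item.
- **Protocol reporting rules.** Protocol section 11: "Data listings will show all recorded data", and "The data will be presented by visit in tables and graphs".
- **Declared deviations.** SAP section 9 names two: the added safety analysis set and the time-off-treatment endpoint that is not reported. The GM-CSF listing rule is not among them.
- **Not stated anywhere.** The LLOQ of the assay, a convention for results below it, and the number of Italian subjects.

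**The concern.** The listing rule selects rows by their result. A result below the LLOQ is a recorded finding, not a missing value, so the SAP's no-imputation statement does not justify leaving it out. For samples taken to characterise systemic safety, a finding of no quantifiable GM-CSF is informative, and it is the one finding that the plan does not show.

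The endpoint is also a before-and-after comparison, and the omission is unlikely to fall evenly on the two sides. If low results sit mainly at the pre-dose time point, the listing will hold mostly unpaired 2-hour values. A reader of the trial report could then state neither how often GM-CSF was quantifiable nor how it changed across a dose.

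**Working it through.** The plan gives no figure to reproduce for this endpoint. The check is mainly textual, with arithmetic on where the omissions would fall.

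**1. Rule against rule.** Protocol section 11 requires listings of all recorded data and presentation by visit in tables and graphs. SAP 7.3 and Listing 16.2.6.9 give a value-restricted listing and nothing else. The words 'all subjects' in the listing title name the population, as SAP 5.1 does for every listing. They do not restore the low samples. SAP section 2 says that deviations from the protocol analysis are highlighted in section 9, and this one is not.

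**2. What an absent row can mean.** Besides a result below the LLOQ, the documents give other routes:
- Some subjects were untreated (SAP 3.2).
- Visits were affected by COVID-19. SAP 5.2 counts missed assessments for six named secondary endpoints, but not for GM-CSF.
- Closing visits follow the Visit 7 schedule (SAP 5.1), which has no PK sample.

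**3. Planned samples.** 2 per visit × 6 visits = 12 samples, or 6 pairs, for a fully sampled Italian subject.

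**4. Which side is at risk.** Protocol 4.1 reports for phase I a peak at 2 hours, a half-life of about 4 hours, and levels back below quantification limits after each dose. The mean peaks given for the 300 µg multiple-dose group are 32 pg/mL (Day 1) and 90 pg/mL (Day 6). If the previous dose was 24 hours earlier, 22 hours pass from peak to the next pre-dose sample:

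C = Cmax × 2^(−22 / half-life)

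- 32 × 2^(−22/4) = 0.7 pg/mL
- 90 × 2^(−22/4) = 2.0 pg/mL
- For assumed half-lives of 3 to 5 hours, the range over both peaks is 0.2 to 4.3 pg/mL.

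The lowest measurable level reported at 300 µg is 3.6 pg/mL. Most pre-dose results would plausibly be below the LLOQ, although the top of the assumed range (4.3) exceeds 3.6. A sample taken before the first dose of an on-treatment week follows seven days off drug, so it would be lower still. The separate statement "GM-CSF was not measurable in serum before trial drug administration" concerns levels before any study drug. It is not evidence about pre-dose levels within a dosing week.

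**5. Rows and pairs that would appear.** Let a and b be the proportions above the LLOQ pre-dose and at 2 hours, assumed independent. Then rows = 6a + 6b and complete pairs = 6ab.

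| a (assumed) | b (assumed) | Rows of 12 | Complete pairs of 6 |
|---|---|---|---|
| 0 | 0.5 to 1.0 | 3 to 6 | 0 |
| 0.1 | 0.5 to 1.0 | 3.6 to 6.6 | 0.3 to 0.6 |
| 0.5 | 0.5 to 1.0 | 6 to 9 | 1.5 to 3.0 |

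**The case against.** The selection is disclosed in the listing title, and every quantifiable exposure is shown, so the plan does not conceal exposure. Nothing says that low results are deleted from the database. Pairs with both values above the LLOQ can be read. Two samples per visit at Visits 1 to 6, together with the listing of visits attended (16.2.5.3), give an approximate denominator. The endpoint is exploratory, confined to Italy and part of a wholly descriptive trial. No dose adjustment or primary result depends on it, and SAP 3.2 says the intermittent regimen will likely not be put forward under posology. All of this stands and limits the weight of the point. The approximate denominator still cannot separate a low result from a sample not taken or not analysed.

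A reader might go further and infer that the listed values would seriously overstate typical 2-hour exposure. The documents do not support that:
- No GM-CSF mean or median is planned, so the bias would arise only if someone summarised the listing.
- Take an assumed lognormal with median 32 pg/mL and log-SD 0.6 to 1.0. Having 30% of 2-hour values below the LLOQ needs an LLOQ of 32 × exp(−0.524 × 0.6) = 23 down to 32 × exp(−0.524 × 1.0) = 19 pg/mL. Having 50% below needs 32 pg/mL. Protocol 4.1 reports measurable levels down to 3.6 pg/mL.
- At a cutoff of 3.6, ln(32/3.6) = 2.185. The share removed is Φ(−2.185/0.6), about 0.01%, to Φ(−2.185/1.0), about 1.4%. The median of the listed values moves from 32 to at most about 32.6 pg/mL.

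**Conclusion.** The point holds as a minor reporting defect. The only GM-CSF output is restricted by result. It conflicts with protocol section 11 and is not declared in SAP section 9. The conflict and the ambiguity of an absent row do not depend on the value of the LLOQ.

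That the loss would fall mainly on pre-dose samples is an inference. It rests on phase I data in healthy adults, first-order decay and a dose 24 hours earlier. The present assay's LLOQ and levels in aPAP patients are not given. The phase I assay quantified 3.6 pg/mL, but its own limit is not stated and may have been lower. The size therefore ranges from no complete pairs, if every pre-dose value is below the LLOQ, to all six if none is and all 2-hour values are quantifiable.

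It would be too strong to say that the endpoint is unreadable or that low results are lost. Complete pairs remain readable, and nothing indicates that the underlying results are discarded.

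**What to change.** - Reword SAP 7.3 and the title of Listing 16.2.6.9 so that every GM-CSF sample from the Italian subjects is listed. Show low results as '<LLOQ' and state the assay's LLOQ.
- Add one small table by visit and time point: samples taken, n (%) above the LLOQ, and median and range with results below the LLOQ ranked lowest. If the median itself falls among those results, report it as '<LLOQ'.
- If the sponsor keeps the restricted listing, declare and explain it in SAP section 9. That would settle the undeclared departure but not the ambiguity of absent rows.

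The cost is one SAP sentence, a listing title and one table. No new data are needed.

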7.4 Handling of Missing Values

No imputation of missing data is planned.

7.5 Multiplicity Adjustments

No multiplicity adjustments are needed since no analyses are to be performed.

7.6 Subgroup and Site Effects

No subgroup analyses are planned.

Adjustments for site effects are not applicable since no analyses are performed.

8 Statistical Methodology for Safety Endpoints

Safety will be considered for subjects included in the Safety Analysis Set. *No imputation of missing data is planned for safety endpoints.*

8.1 Safety Parameters

The safety parameters are

- Adverse events
- Physical examination
- Vital signs
- ECG
- Laboratory safety assessments
- CT scan

8.1.1 Analysis and Presentation of Safety Parameters

8.1.2 Adverse Events

All adverse events (AEs) occurring after informed consent will be reported in the eCRF. AEs will be coded using the Medical Dictionary for Regulatory Activities (MedDRA) version 21.0.

Adverse events are considered treatment emergent if the onset of the events is on or after the first exposure date of IMP in this trial and until (estimated) last drug date + 7 days. Last drug date is defined as last kit date + 21 days or end of trial date whatever comes first. Only treatment emergent events will be included in the safety summaries.

Possible or probable related AE's are defined as ADRs.

Adverse events will be presented as described in section 7.1.

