10.3. Medical History

Medical history assessment will be assessed at Baseline (Visit 1).

AEs that occurred during previous treatment with inhaled molgramostim, were reported as AEs in IMPALA, and are still ongoing, will be recorded as medical history. AEs that occurred after completion of IMPALA but still had a reasonable time-relationship to inhaled molgramostim treatment, and were not reported in IMPALA, and are still ongoing, will be reported as AEs at Baseline (Visit 1).

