11.1. Primary Endpoints

Number of AEs, SAEs, ADRs, and AEs leading to treatment discontinuation.

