3.3 Subject included

No formal sample size calculation was done as this is an open-label extension trial.

Subjects with aPAP who have completed the IMPALA (MOL-PAP-002) trial will be eligible for this trial. Up to 90 subjects may be included. All subjects in need of treatment will receive inhaled molgramostim.

4 Analysis Sets

All subjects excluding screening failures will be included in the full analysis set.

All subjects with exposure within the trial will be included in the safety analysis set.

The full analysis set will be used for demographics and efficacy summaries and the safety analysis set will be used for safety summaries.

Only recorded data will be analyzed/presented and any subjects who have missing data will only have observed data reported, with no imputation for missing data.

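### Suspected carry-over events that the protocol collects as AEs at Visit 1 reach no AE table, and the SAP does not declare the restriction

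*SAP*

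**What the plan says.** **Protocol 10.3 (Medical History)** sorts events that are ongoing at entry into two classes. Events already reported in IMPALA become medical history. The other class is "AEs that occurred after completion of IMPALA but still had a reasonable time-relationship to inhaled molgramostim treatment, and were not reported in IMPALA"; if still ongoing, these are to be reported as AEs of this trial at Visit 1.

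**Protocol 11.1** gives the primary endpoint as "Number of AEs, SAEs, ADRs, and AEs leading to treatment discontinuation". It sets no treatment-emergent condition.

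**SAP 8.1.2** calls an event treatment emergent if "the onset of the events is on or after the first exposure date of IMP in this trial", up to a cut-off after the last drug date, and adds: "Only treatment emergent events will be included in the safety summaries".

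**SAP section 4 (Analysis Sets)** fixes the population for those summaries: "All subjects with exposure within the trial will be included in the safety analysis set".

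**SAP section 9 (Deviations from Protocol)** declares two things: the added safety analysis set, and the decision not to report time off treatment. The treatment-emergent restriction is not mentioned.

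**The concern.** The sponsor chose to treat a particular kind of between-trial event as an AE of this extension and not as background history. The SAP's onset rule then keeps that same kind of event out of every tabulated count. By the protocol's own definition these events were not reported in IMPALA, so on these documents no planned table in either trial is shown to contain them.

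The primary objective is the safety of long-term use. Events selected for their timing relative to the drug are relevant to it, even though they are suspected and not established reactions. The omission works in one direction: leaving them out can lower the tabulated AE, SAE and ADR counts but cannot raise them. A reader working from the tables would not know that the class exists, and the SAP's list of departures from the protocol would not alert them.

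**Working it through.** The plan gives no figure to reproduce, so the check follows one event of the protocol 10.3 class through the SAP.

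1. **Onset against the window.** The event began after IMPALA and is already present at Visit 1, so its onset is no later than Visit 1. First exposure in this trial is at Visit 1 (protocol 9.5) or later, because protocol 6.1 lets subjects enter untreated and start afterwards. Hence onset ≤ Visit 1 ≤ first exposure. The SAP 8.1.2 condition (onset on or after first exposure) can be met only if all three fall on the same day.

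2. **Tables.** SAP section 13 lists AE Tables 14.3.1.1 to 14.3.1.23, which is 23 tables. Tables 14.3.1.2 to 14.3.1.23 (22 tables) are titled treatment emergent. The other, the overview in Table 14.3.1.1, lacks the label but is a safety summary and so falls under the 8.1.2 sentence. The class enters 0 of 23.

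3. **Second route of exclusion.** All 23 tables use the safety analysis set. A subject who brought in such an event and was never dosed in this trial is outside that set. SAP section 9 confirms that some subjects are untreated. SAP 3.2 reports 5 of 60 not receiving treatment at termination, but does not say how many were never dosed, so the size of this group is not stated.

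4. **Listings.** SAP 5.1 bases all listings on all subjects. Listings 16.2.7.1 to 16.2.7.4 (AEs, SAEs, ADRs, and AEs leading to treatment discontinuation) carry no treatment-emergent label. The events should be found there.

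5. **Partial recapture.** Under protocol 10.9.2.1 a change in severity is reported as an AE of new severity. If that happens after first dosing, the new record could count as treatment emergent. This recovers only events that change severity.

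6. **How the SAP treats lavage over the same interval.** SAP 7.2.4 plans a separate summary of whole lung lavage between IMPALA and this trial (Table 14.2.4.1), and SAP 5.3 lists the days between IMPALA completion and Visit 1. The SAP therefore recognises the gap but has no equivalent for AEs.

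7. **Size.** The documents give neither the number of subjects with a gap nor the number of events. If Visit 1 coincides with the final IMPALA visit, which note a of the flow chart allows, the class is empty for that subject. The only available scale is the 60 enrolled: one affected subject is 1/60 = 1.7%. That describes any one subject and does not say how many are affected.

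**The case against.** **The endpoint need not include these events.** The protocol synopsis counts AEs occurring in the course of the trial, and a gap event starts before it. Protocol section 11 leaves analytic detail to the SAP, and excluding pre-dose onsets is common practice. It also keeps the event rates of SAP 7.1 consistent with exposure, which SAP 6.1 counts from Visit 1. This stands as a reason not to mix gap events into the treatment-emergent tables or rates. It does not explain why events that the protocol expressly makes AEs of this trial, after earlier exposure to the same product, should have no summary at all, or why the restriction goes undeclared.

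**The events are reported, in listings.** This stands. They are absent from the tables, not from the report.

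**Other analyses may pick them up.** Protocol section 11 plans a separately reported combination with IMPALA data. Its AE rules, and IMPALA's own follow-up and post-trial reporting rules, are not in these documents. It therefore cannot be shown that the events are lost everywhere, only that nothing here admits them to a table.

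Some stronger readings are tempting but unsupported:

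- *That the omission decides which terms reach the 5% tables.* Three of 60 is 5%, but Tables 14.3.1.3 and 14.3.1.12 use the safety set, whose size is not given. They are properly restricted to treatment-emergent events and would not change under the remedy.
- *That gap events resolved before Visit 1 are never recorded.* Protocol 10.3 assigns ongoing events; nothing confines medical history to ongoing conditions.
- *That subjects who did not re-start are most affected.* No data in the documents bear on this.
- *That these are drug reactions.* Protocol 10.3 requires a reasonable relationship in time, not causality.

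**Conclusion.** The point holds as a gap in tabulation and an undeclared narrowing of the primary endpoint. Events that protocol 10.3 makes AEs of this trial at Visit 1 enter none of the 23 AE tables, apart from same-day onsets and later severity changes, and SAP section 9 does not say so. It does not show that the treatment-emergent convention is wrong or that the events are concealed.

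The effect is probably small, and zero for subjects who rolled over without a gap. The conclusion rests on three assumptions: that the 8.1.2 sentence governs Table 14.3.1.1 despite its title; that the all-subject AE listings hold every recorded AE, as SAP 5.1 and the listing titles indicate; and that the class is not empty, which the documents cannot confirm. The change is worth making because safety is the primary objective and the cost is low.

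**What to change.** 1. Leave the treatment-emergent definition, its tables and the exposure-based rates unchanged.
2. In SAP 7.1 and 8.1.2, add one summary of AEs reported at Visit 1 under protocol 10.3, by SOC and PT, seriousness and relationship, with those judged possible or probable shown as ADRs. Select them as AE records with a start date before Visit 1. Using first exposure as the cut-off would also bring in events that began in this trial while a subject was still untreated.
3. Base the summary on the full analysis set, so that subjects never dosed in this trial are included. It would parallel the between-trial lavage summary in Table 14.2.4.1, although that table uses the safety set.
4. Show the same events as a separate, labelled row in Table 14.3.1.1, outside the rates.
5. State in SAP section 9 that the AE summaries are restricted to treatment-emergent events, whereas the protocol's primary endpoint is not.

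The cost is one extra table, one row and a short addition to the text, from data that the protocol already requires in the eCRF. Reported AE and ADR counts may be slightly higher. Amending protocol 10.3 is not proposed: SAP version 3.0 is dated 21JAN2021, after the decision to stop the trial, so changing a Visit 1 collection rule would yield no data without going back to the sites.
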